7.1.4 Efficacy Variables

Analysis of Primary Efficacy Endpoint

The primary efficacy endpoint is a composite variable consisting of the longer of either (1) length of time on mechanical ventilation or (2) length of time of inotrope use.

The definition of mechanical ventilation includes invasive mechanical ventilation or non-invasive mechanical ventilation including BPAP or CPAP. Length of time on mechanical ventilation will be measured until the subject is discharged from the hospital or at Day 28. The length will be derived as the time in hours from separation from CPB until discontinuation of all mechanical ventilation including non-invasive support. If invasive or non-invasive mechanical ventilation is stopped but has to be restarted, time will continue to accrue. If a subject did not receive any mechanical ventilation the length is set to 0. For subjects who died before discharge from the hospital or before Day 28, respectively, the observed length of time on mechanical ventilation will be used. As sensitivity analyses subjects who died will (1) be excluded from analysis and (2) be assigned a length of time on mechanical ventilation of 28 days.

Asklepion GROWTH HEALTH PINNOVATION

11 August 2017

The definition of inotrope use includes medications which are considered within the derivation of the total inotrope score (dopamine, dobutamine, milrinone, epinephrine, phenylephrine, norepinephrine). Length of inotrope use will be measured until the subject is discharged from the hospital or until Day 28, whichever occurs first. The length will be derived as the time of first use until last use (in hours). Any duration of re-use will continue to accrue. If a subject did not use any inotropes the length is set to 0. For subjects who died before discharge from the hospital or before Day 28, respectively, the observed length on inotropes will be used. As sensitivity analyses subjects who died will (1) be excluded from analysis and (2) be assigned a length of time on inotropes of 28 days.

Hypothesis to be tested:

H0: Composite endpoint within the L-citrulline group is equal to that of the placebo group

H1: Composite endpoint within the L-citrulline group is unequal to that of the placebo group

H0 will be tested using a Wilcoxon-rank-sum test.

The level of significance is 1% (two-sided).

The FAS will be the primary analysis set for the analysis on the composite endpoint. Analyses using the mFAS and the PP serve as sensitivity analyses.

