4.4 Efficacy Analysis

4.4.1 Analysis of Primary Efficacy Variable

The primary efficacy endpoint is a composite variable consisting of the longer of either (1) length of time on mechanical ventilation or (2) length of time of inotrope use.

The definition of mechanical ventilation shall include invasive mechanical ventilation or non-invasive mechanical ventilation including BPAP or CPAP. The definition of inotrope use includes medications which are considered within the derivation of the total inotrope score (dopamine, dobutamine, milrinone, epinephrine, phenylephrine, norepinephrine).

The length of time on mechanical ventilation will be measured until the subject is discharged from the hospital or at Day 28. The length will be derived as the time in minutes from separation from CPB (variable "End time" of parameter "CPB" from section "Post incision" on CRF "Surgery") until discontinuation of all mechanical ventilation including non-invasive support (variables "Stop Time/Date of last use of non-invasive ventilation" and "Stop Time/Date of last use of invasive ventilation" of parameter "CPB" from section "Post incision" on CRF "Mechanical ventilation"). If invasive or non-invasive mechanical ventilation is stopped but has to be restarted, time will continue to accrue by subtracting the total duration of all ventilation breaks (variables "Stop date/time" and "Restart date/time" from CRF "Ventilation breaks").

- Length of time on mechanical ventilation (min) =
(Time mechanical ventilation discontinuation - End time (CPB) + 1) -
sum of all ventilation breaks with any ventilation break = Restart time - Stop time + 1

If a subject did not receive any mechanical ventilation the length is set to 0. For subjects who died before discharge from the hospital or before Day 28, respectively, the observed length of time on mechanical ventilation will be used. As sensitivity analyses subjects who died will (1) be excluded from analysis and (2) be assigned a length of time on mechanical ventilation of 28 days.

Length of time of inotrope use will be measured until the subject is discharged from the hospital or until Day 28, whichever occurs first. The length will be derived as the time in minutes from separation from CPB (variable "End time" of parameter "CPB" from section "Post incision" on CRF "Surgery") until last use (last "end date/time" of any medication as documented in section "Inotropes" on CRF "Inotropes and Vasoactive Medications").

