4.4.2 Analysis of Secondary Efficacy Variables

No formal statistical hypotheses are specified for the secondary endpoint variables. Nonetheless statistical testing methods will be applied to compare treatment groups. A significance level of 5% (two-sided) will be used for such analyses. Secondary efficacy endpoints will be analyzed using FAS, mFAS and PP. All secondary analyses are considered exploratory.

Length of time on mechanical ventilation

The same definitions and analyses as described for the primary endpoint will be applied. As sensitivity analysis, length of time on mechanical ventilation will be calculated starting on “start date/time” of mechanical ventilation.

Length of time on positive pressure (non-invasive) ventilation

Positive pressure ventilation describes non-invasive mechanical ventilation. The same definitions (only using non-invasive ventilation stop date/time and non-invasive ventilation breaks: BPAP, CPAP, HFNC, and other non-invasive) and analyses as described for the primary endpoint will be applied.

Length of time of inotrope use

The same definitions and analyses as described for the primary endpoint will be applied. As sensitivity analysis, length of time of inotrope use will be calculated starting on first “start date/time” of inotrope use.

Inotrope score

The total inotrope score at each hour post-operatively from the time of separation from bypass until the completion of study drug will be calculated as:

Total Inotrope Score = Dopamine + Dobutamine + 10*Milrinone + 100*Epinephrine +100*Phenylephrine + 100*Norepinephrine.

The score will be calculated for each hour post separation from CPB (see section 4.4.1) until 48 hours post separation. If within the time interval of hours x after the separation from CPB any inotrope was given, the total score will be calculated and used for analysis.

Example for a patient's inotrope documentation:

- 12:00: Separation from CPB
- Dopamine: 100 mcg/kg/min from 12:00 to 13:00,
- Dobutamine 100 mcg/kg/min from 13:00 to 13:30, 14:01 to 14:59, and 16:00 to 17:00.

The times of interest at 1, 2, 3, ... hrs will be derived as time of separation from CPB + 59, 119, 179, ... minutes. I.e., the times of interest and the total inotrope score would then be calculated as follows:

- 1 hrs (12:00-12:59) = 100 (Dopamine (100) documented 12:00-13:00)
- 2 hrs (13:00-13:59) = 200 (Dopamine (100) documented 12:00-13:00
Dobutamine (100) documented 13:00-13:30)

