The same definitions (only using invasive ventilation stop date/time and invasive ventilation breaks: FVS, PVS and other invasive) and analyses as described for the primary endpoint will be applied.

Length of PICU stay

The length of PICU stay will be calculated as the total number of days postoperative until discharge from PICU. The length will be derived as the number of days from day after surgery (variable "Date of surgery" on CRF "Surgery" + 1) until discharge from PICU (variable "Date transferred to floor" on CRF "Post-operative observation"). If subject has to be readmitted to PICU, time will continue to accrue (variables "Date of readmission" and "Date transferred to floor" (second assessment) from CRF "Post-operative observation").

- Length of PICU stay (days) =
(Date transferred to floor - (Date of surgery + 1) + 1) +
(Date transferred to floor (2nd assessment) - Date of readmission + 1)

For subjects who died before discharge from PICU or before Day 28, respectively, the observed length of PICU stay will be used. As sensitivity analyses subjects who died will (1) be excluded from analysis and (2) be assigned a length of PICU stay of 28 days.

For the length of PICU stay the same analyses as described for the primary endpoint will be applied.

Length of time on vasodilators

Length of time on vasodilators will be measured from first use following separation from bypass, until the subject is discharged from the hospital or at Day 28. The length will be derived as the time in minutes from separation from CPB (variable "End time" of parameter "CPB" from section "Post incision" on CRF "Surgery") until last use (last "end date/time" of any medication as documented in sections "Vasodilators" or "Other vasodilators" on CRF "Inotropes and Vasoactive Medications").

- Length of time of vasodilators (min) =
Last "end date/time" of any vasodilators - End time (CPB) + 1

Any interruptions will discontinue to accrue, any duration of re-use of vasodilators will continue to accrue. If a subject did not use any vasodilators the length is set to 0. As a sensitivity analysis, subjects with no use of vasodilators will be excluded. For subjects who died before discharge from the hospital or before Day 28, respectively, the observed length of time on vasodilators will be used. As sensitivity analyses subjects who died will (1) be excluded from analysis and (2) be assigned a length of time on vasodilators of 28 days.

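### SAP 4.4.1 subtracts every ventilation break without requiring the child to be off both modes; if breaks are logged within mode, supported time is lost from the primary variable

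*SAP*

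**What the plan says.** SAP 4.4.1 defines the primary endpoint as a "composite variable consisting of the longer of either (1) length of time on mechanical ventilation or (2) length of time of inotrope use". On the first component it says: "The definition of mechanical ventilation shall include invasive mechanical ventilation or non-invasive mechanical ventilation including BPAP or CPAP". Protocol 7.1.4 runs the interval "from separation from CPB until discontinuation of all mechanical ventilation including non-invasive support", and SAP 4.4.1 keeps that end point.

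For interruptions, SAP 4.4.1 says: "If invasive or non-invasive mechanical ventilation is stopped but has to be restarted, time will continue to accrue by subtracting the total duration of all" breaks, using the stop and restart times on the CRF page for ventilation breaks. The formula takes the span from the end of bypass to the end of ventilation, plus one minute, and subtracts the "sum of all ventilation breaks with any ventilation break = Restart time - Stop time + 1".

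Two secondary endpoints in SAP 4.4.2 use the same derivation restricted by mode. Length of intubation is derived "only using invasive ventilation stop date/time and invasive ventilation breaks: FVS, PVS and other invasive". Length of positive pressure ventilation uses "non-invasive ventilation breaks: BPAP, CPAP, HFNC, and other non-invasive".

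Neither document says that a break means time off all support. SAP section 5, on changes from the protocol, does not mention breaks.

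**The concern.** The definition and the formula in SAP 4.4.1 do not match. By definition, a child on CPAP after extubation is still on mechanical ventilation. The trigger for a break, however, is a stop and restart of either mode, and every break is summed. A gap in intubation filled by CPAP is an interruption of one mode, not of ventilation, but the formula as worded can subtract it. The same holds for a gap in CPAP filled by re-intubation. Where an invasive and a non-invasive break overlap, the common time comes off twice.

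Any shortening would fall on children who alternate modes or are re-intubated. The protocol foresees re-intubation: Table 1 lists it among events associated with this surgery. Sensitivity analyses (1) to (4) in SAP 4.4.1 concern deaths and start times, so none would reveal the problem. If the interim sample size re-estimation uses the same derivation, shortened long durations could also enter the re-estimated variance.

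**Working it through.** **The plan's own figure.** SAP 1.3 gives 92 per group for a two-sided Wilcoxon rank-sum test at 0.01, 90% power and effect size 0.600. Noether's formula, with p = Φ(0.6/√2) = 0.6643, gives n = (2.576 + 1.282)² / [6 × (0.6643 − 0.5)²] = 91.85, rounded up to 92. The figure reproduces. It does not depend on the break rule, so the planned N is unchanged.

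**Inputs for the check.** The formula is from SAP 4.4.1: length = (end of ventilation − end of CPB + 1) − Σ(restart − stop + 1), in minutes. The histories below are illustrations, not trial data. Time 0 is separation from bypass.

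**If breaks are logged within mode:**

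1. Intubated 0-24 h, CPAP 24-48 h, re-intubated 48-120 h. The span is 7,201 min and the invasive break 1,441 min. The formula gives 7,201 − 1,441 = 5,760 min = 96 h. Time on support is 120 h.
2. Intubated 0-24 h, CPAP 24-48 h, off 48-60 h, re-intubated 60-132 h, CPAP 132-156 h. The invasive break is 24-60 h (36 h) and the non-invasive break 48-132 h (84 h). The formula gives 156 − 36 − 84 = 36 h, ignoring the one-minute terms. Time on support is 156 − 12 = 144 h. The 120 h removed comprise 12 h truly off support, the same 12 h again, 24 h on CPAP and 72 h intubated.
3. Intubated 0-1 h, CPAP 1-2 h, off 2-20 h, intubated 20-21 h, CPAP 21-22 h. The formula gives 1,321 − 1,141 − 1,141 = −961 min. Time on support is 4 h.
4. Intubated 0-12 h, off 12-36 h, intubated 36-60 h, CPAP 60-61 h. The formula gives 3,661 − 1,441 = 2,220 min = 37 h, which equals time on support. Re-intubation with no support in between is scored correctly.

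**History 1 under each logging convention:**

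| Breaks logged | Primary formula (actual 120 h) | Intubation formula (actual 24 + 72 = 96 h) |
|---|---|---|
| Within mode | 96 h, wrong | 7,201 − 1,441 = 5,760 min = 96 h, right |
| Only when off all support | 7,201 − 0 = 7,201 min, about 120 h, right | 7,201 − 0 = 7,201 min, about 120 h, wrong |

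Neither row makes both formulas correct.

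**Effect on the composite.** The composite is the longer of ventilation and inotrope time, and the fault only shortens ventilation time. It therefore changes a child's value only when correct ventilation time exceeds inotrope time. A negative ventilation length would not itself show in the composite: a child with history 3 and no inotropes has inotrope time set to 0, so the composite is max(−961, 0) = 0, the same as a child never supported.

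**The case against.** The strongest objection is that everything turns on a CRF page that is not in the documents. SAP 4.4.1 names one page with one pair of times. If sites entered a break only when the child was off all support, the primary formula is correct. A single off-support log carrying a mode label would also fit the wording of 4.4.2. The definition within 4.4.1 favours that reading, because a child on CPAP is not on a break from ventilation so defined. A rule that can return a negative length is unlikely to be what was meant, and data cleaning or the blind data review might catch it.

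Much of this stands. A reader might infer that CPAP time is certainly removed from the primary variable; the documents support this only if breaks are logged within mode. The benign convention does not clear the plan, however, because it moves the error to the intubation endpoint. Review might catch a negative ventilation length, but histories 1 and 2 yield plausible positive values that nothing would flag.

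A reader might also infer bias toward no effect, since the one re-intubated child in the Phase IB study was on placebo (Protocol 1.4 and 7.2). That is one child among 22, and the documents do not say that the child had CPAP between intubations, which the fault requires. The rule is the same in both arms, and the rank test limits the influence of a few shortened values.

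**Conclusion.** The point holds as a conditional one. SAP 4.4.1 lacks a definition of a break that matches its definition of mechanical ventilation, and it lacks an overlap rule. If breaks are logged within mode, as the wording of 4.4.2 suggests without proving, the primary variable loses supported time: 24 of 120 h in history 1 and 108 of 144 h in history 2. If breaks are logged only when the child is off all support, the primary variable is right and the intubation endpoint is wrong. Sections 4.4.1 and 4.4.2 therefore cannot both be right under one convention.

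The primary endpoint is affected only in children with a break in one mode bridged or overlapped by the other, and only where correct ventilation time exceeds inotrope time. The documents do not give their number or their split between arms, so neither the size nor the net direction of any bias in the treatment comparison can be determined. The change should be made because the ambiguity sits in the primary variable and is cheap to remove.

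**What to change.** Before unblinding, amend SAP 4.4.1 to say that:

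- a break for the primary endpoint is an interval with neither invasive nor non-invasive ventilation, so that only time off both modes is subtracted, and subtracted once;
- ventilation ends at the later of the last invasive and last non-invasive stop times.

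Keep mode-specific breaks only for the secondary endpoints in 4.4.2, and state there how breaks are logged.

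It should not be assumed that every time needed is already on the CRF. SAP 4.4.1 names last-stop times, break times and a start of mechanical ventilation, but no separate start for each mode. Where a start is missing, the ventilator settings recorded about every hour (Protocol 5.1.2.2 onward) can establish whether the child was on the other mode, to roughly that precision.

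The cost is a short SAP amendment and a small amount of extra programming and data checking. The endpoint itself does not change; the amendment restores the protocol's definition of time on ventilation.

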7.4 Interim Analysis

One interim analysis is planned to be carried out when the first 95 consecutively randomized full analysis set (FAS)-patients (i.e. 50% of the planned patients) will have undertaken their Follow up visit (Day 28 or Hospital Discharge), data required for the analysis of the composite endpoint have been entered into the eCRF, and those data have been cleaned appropriately. Only a sample size re-estimation will be carried out during this interim analysis; no other statistical analyses will be conducted. The sample size re-estimation will be done by an independent, unblinded statistician following the same procedures and criteria as for the initial

sample estimate, as described in section 7.2. Only the results of the sample size re-estimation will be provided to Asklepion.

Only the re-estimated variance values will be used for sample re-calculation, while the assumed values will not be re-estimated but kept as described in Section 7.2.

In the event that the sample size re-estimation leads to a reduction of the sample size due to lower re-estimated variance compared to the assumed variance values, the sample size as currently planned will be kept, and not reduced, to ensure robust estimations for safety and efficacy variables.

If the trial is to be continued with the re-estimated sample size, an appropriate protocol amendment will be submitted to the FDA as soon as feasible.

Final analysis will be based on the population of all randomized patients without taking the sample size re-estimation results into consideration. Due to the fact that only the interim variance will be assessed, no alpha adjustment of statistical analyses is required.

8 Quality Assurance and Quality Control

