1.4 Interim Analysis

One interim analysis is planned to be carried out when the first 95 consecutively randomized FAS patients (i.e. 50% of the planned patients) will have undertaken their Follow-Up Visit (Day 28 or Hospital Discharge), data required for the analysis of the composite endpoint have been entered into the eCRF, and those data have been cleaned appropriately (See external sample size reestimation document). During this interim analysis, only a sample size re-estimation will be carried out. No other statistical analyses will be conducted. The sample size re-estimation will be done by an independent, unblinded statistician following the same procedures and criteria as for the initial sample size estimate. Only the re-estimated variance values will be used for the sample re-calculation, while the assumed mean values will not be re-estimated but kept. Only the results of the sample size re-estimation will be provided to Asklepiion Pharmaceuticals.

In the event that the sample size re-estimation leads to a reduction of the sample size due to lower re-estimated variance compared to the assumed variance values the sample size as currently planned will be kept but not reduced to ensure robust estimations for safety and efficacy variables. If the trial is to be continued with the re-estimated sample size, an appropriate protocol amendment will be submitted to the Food and Drug Administration (FDA) as soon as feasible.

Final analysis will be based on the population of all randomized patients without taking the sample size re-estimation results into consideration. Due to the fact that only the interim variance and mean values will be assessed, no alpha adjustment of statistical analyses is required.

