3.4 Per-Protocol Set

The per-protocol set (PP) includes all subjects included in the SAF who had no significant protocol deviations and completed through Day 28 or until discharge from the hospital (end of study follow-up). Protocol deviations will be identified and classified for each subject during a blind data review meeting. For the PP all subjects will be assigned to the treatment actually received.

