- Length of time of inotrope use (min) =
Last "end date/time" of any inotrope - End time (CPB) + 1

Any interruptions will discontinue to accrue, any duration of re-use will continue to accrue. If a subject did not use any inotropes the length is set to 0. For subjects who died before discharge from the hospital or before Day 28, respectively, the observed length on inotropes will be used.

As sensitivity analyses subjects who died will (1) be excluded from analysis and (2) be assigned a length of time on inotropes of 28 days. Hypothesis to be tested:

H0: Composite endpoint within the L-citrulline group is equal to that of the placebo group

H1: Composite endpoint within the L-citrulline group is unequal to that of the placebo group

H0 will be tested using a Wilcoxon-rank-sum test. The level of significance is 1% (two-sided).

As additional sensitivity analyses, the composite endpoint will be derived with (3) length of time of inotrope use starting on first "start date/time" of inotrope use and (4) length of time of inotrope use starting on first "start date/time" of inotrope use and length of time on mechanical ventilation starting on "start date/time" of mechanical ventilation. For sensitivity analyses (3) and (4) the observed length on mechanical ventilation/ inotropes will be used for subjects who died.

The FAS will be the primary analysis set for the analysis on the composite endpoint. Analyses using the mFAS and the PP serve as sensitivity analyses.

Two-sided 95% confidence intervals using Hodges-Lehman method will be additionally calculated.

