Survival analyses using Kaplan-Meier estimates and plots, log-rank test (significance level of 5%) and Cox-regression modeling including factor treatment (no further factors to be included) will serve as sensitivity analyses. For subjects who died before discharge from the hospital or before Day 28, respectively, the observed length of time on mechanical ventilation/inotropes will be used. The sensitivity analyses (1) and (2) as described for the primary analysis (subjects who died will (1) be excluded from analysis and (2) be assigned a length of time on inotropes of 28 days) will not be applied for survival analyses. The sensitivity analyses (3) and (4) as described for the primary analysis (composite endpoint will be derived with (3) length of time of inotrope use starting on first "start date/time" of inotrope use and (4) length of time of inotrope starting on first "start date/time" of inotrope use and length of time on mechanical ventilation starting on "start date/time" of mechanical ventilation) will be applied for survival analyses. For survival analyses different sets of analyses will be done:

(1) The composite variable for subjects without any mechanical ventilation and without any use of inotropes is set to 0, observations will not be censored

(2) The composite variable for subjects without any mechanical ventilation and without any use of inotropes is set to 0, observations will be censored

(3) Subjects without any mechanical ventilation and without any use of inotropes will be deleted from analysis

For sensitivity analyses (3) and (4) the first set of analyses (i.e., (1) The composite variable for subjects without any mechanical ventilation and without any use of inotropes is set to 0, observations will not be censored) will be used.

Subjects who receive mechanical ventilation or are still using inotropes on the last day of observation (which can be Day 28, Day of early discontinuation, or Day of death) will be censored for survival analyses.

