4.8 Missing Values

Efficacy endpoints describing length of time

If a subject did not receive any mechanical ventilation / inotropes / positive pressure ventilation / intubation / vasodilators / chest tube, the corresponding length of time is set to 0. For subjects who died before discharge from the hospital or before Day 28, respectively, the observed length of time will be used for analysis of all time variables.

For time to event analyses censoring information will be used for statistical analyses.

No other imputation of missing values will be used.

Efficacy endpoint inotrope score

The total inotrope score will be set to zero after the bypass pump has been removed. It will also be set to zero for patients not using inotropes at all.

Further secondary efficacy endpoints

No imputation of missing values will be applied for the secondary endpoints hemodynamic improvement, volume of chest tube drainage, and L-citrulline plasma levels.

Safety endpoints

For laboratory data, concentrations below the limit of quantification will be set to zero. Missing safety data or safety assessments will not be estimated nor imputed. All safety summaries and analyses will be based on observed data.

No other imputation of missing values will be used.

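### The primary Wilcoxon test scores a child who dies at the observed time on support, so a death at about 6 h can rank better than most survivors; the 28-day rule that prevents this is only a sensitivity analysis

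*SAP*

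**What the plan says.** SAP 4.4.1 defines the composite as the longer of time on mechanical ventilation and time on inotropes, and tests it by a Wilcoxon rank-sum test at two-sided 1%. For a child who dies before discharge or Day 28, "the observed length of time on mechanical ventilation will be used" for ventilation and "the observed length on inotropes will be used" for inotropes. SAP 4.8 makes this general: "the observed length of time will be used for analysis of all time variables". Protocol 7.1.4 has the same rules.

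Two alternatives are prespecified as Wilcoxon sensitivity analyses: (1) exclude children who died; (2) give them 28 days. The SAP states that neither carries over to the time-to-event analyses; of the second it says "be assigned a length of time on inotropes of 28 days) will not be applied for survival analyses". There, a child still on support on the last day observed, including the "Day of early discontinuation, or Day of death) will be censored for survival analyses".

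Deaths are also shown by arm as adverse events leading to death (SAP 4.5) and as 28-day mortality, an exploratory percentage (SAP 4.6).

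**The concern.** Death stops the clock on both components. With shorter times favourable, a child who dies on support a few hours after bypass receives a low, hence good, rank. The SAP handles that same value differently in its survival analyses, where it is censored as incomplete; the primary test ranks it as a completed duration.

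Of the planned analyses of the composite, only rule (2) ranks a death as a bad outcome:

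- Rule (1) removes the child.
- The survival analyses censor deaths on support and count deaths after weaning as events.
- Sensitivity analyses (3) and (4) keep the observed length.
- The per-protocol set (SAP 3.4), read literally, drops children who did not complete follow-up.

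If several very early deaths fell mainly on L-citrulline, they would move the primary decision towards benefit. The same deaths on placebo would move it away.

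**Working it through.** **Inputs from the documents.** Pilot placebo composite: mean 44.4 h, SD 63.62 h, N = 11 (Protocol 7.2, Table 2). Planning values: means 44 and 14, SD 50, two-sided 1%, power 90%, 92 per group (SAP 1.3). Limit of follow-up: 28 days = 672 h. Interim: first 95 FAS patients (SAP 1.4).

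**Assumptions.** The distribution shapes, a 40% shortening on drug as a smaller-than-planned effect, the share of zero durations, and all death counts and times. The documents state no expected mortality, and the pilot had no deaths (Protocol 1.5).

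**1. The plan's sample size.** Noether: n = (2.576 + 1.282)² / [6(p − 0.5)²] with p = Φ(0.6/√2) = 0.6643. This gives 91.9, so 92 per group, as stated.

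**2. Lognormal fit.** σ² = ln(1 + (63.62/44.4)²), so σ = 1.056. μ = ln 44.4 − σ²/2 = 3.235, so the placebo median is 25.4 h. Drug durations are placebo durations times a ratio r.

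**3. Share of survivors, arms pooled, who rank worse than a death on support at time t.** Share = ½[Φ((μ − ln t)/σ) + Φ((μ + ln r − ln t)/σ)]. For t = 6 and r = 0.6: ½(0.914 + 0.811) = 86%.

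| Death at | r = 0.6 | r = 14/44 | r = 14/44, 20% zero durations | gamma, 44 v 14, SD 50 |
|---|---|---|---|---|
| 6 h | 86% | 76% | 61% | 51% |
| 12 h | 68% | 56% | 45% | 43% |
| 24 h | 43% | 34% | 27% | 33% |

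The third column is 0.8 times the second. Fitting each arm to its own pilot mean and SD with four shapes gives 69-83% at 6 h and 52-63% at 12 h. Of the shapes tried, only a normal at planning values, which puts mass below zero, exceeds half at 24 h (54%).

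**4. When a drug-arm death helps the drug.** It is neutral when it beats as many placebo survivors as a drug survivor does on average. This gives t* = 25.4 × r^(1/√2): 17.7 h at r = 0.6 and 11.3 h at r = 14/44.

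**5. Effect on the decision.** Simulated P(significant benefit), 92 per arm, r = 0.6, deaths at 6 h, at least 20,000 runs per case (standard error about 0.3 points).

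| Deaths, drug v placebo | Observed length | Worst rank |
|---|---|---|
| none | 72% | 72% |
| 1 v 0 | 75% | 66% |
| 2 v 2 | 70% | 68% |
| 3 v 1 | 76% | 57% |
| 4 v 0 | 82% | 46% |
| 0 v 4 | 55% | 84% |

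Excluding the deaths in the 4 v 0 case gives about 70-72%. Moving those four deaths later, observed length gives about 77% at 12 h, 72% at 18 h and 68% at 24 h. At 44 v 14 every case gives about 100% under both rules.

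**6. No effect on duration.** With four deaths at 6 h on drug only, the false-benefit rate is about 1.4% under observed length and about 0.1% under worst rank, against 0.5% nominal. With equal 2% mortality in both arms it is 0.49% and 0.51%.

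**7. Sample size re-estimation if a death were entered at 672 h.** Take arms of 48 and 47, means 44 and 14, SD 50.

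- Death on placebo: variance = [92 × 2,500 + 628² × 47/48]/93 = 6,625, SD 81.4.
- Death on drug: variance = [92 × 2,500 + 658² × 46/47]/93 = 7,030, SD 83.8.

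The formula in step 1, with 30/SD in place of 0.6, then gives 235 and 249 per group instead of 92.

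**The case against.** The strongest reply is that the plan already deals with this. Exclusion, 28-day assignment and a censored log-rank analysis are prespecified, none of them rewards an early death, and deaths are reported by arm, so an imbalance could not stay hidden. Observed time on support also fits the objective in Protocol 2.1, which is the need for ventilation and inotropes. Much of this stands: the point is about which rule carries the 1% decision. But the objective does not explain why a value censored as incomplete in one analysis should count as a short, successful duration in the primary one.

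Four stronger readings are tempting, and the documents do not support them.

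- **That any death at 6 to 12 h beats most survivors.** This is secure at 6 h only; at 12 h the share falls below half under two of the four scenarios tabulated.
- **That the gap between 82% and 46% measures distortion by the current rule.** Against 72% with no deaths, the current rule adds about 10 points. The other 26 are the penalty that worst rank imposes.
- **That type I error is generally inflated, or never affected.** It is unaffected when mortality is equal and rises when early deaths fall on drug alone.
- **That the per-protocol analysis certainly omits deaths.** Membership is settled at the blind data review meeting (SAP 4.9).

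Four deaths within hours in one arm is also an extreme case: 4/92 = 4.3%. Children needing preoperative ventilation or inotropes are excluded (Protocol 4.3.3).

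**Conclusion.** The concern holds in a limited form. The primary scoring lets a very early death on support count as a good result, and the one analysis that ranks death as bad is secondary to it. The consequence is material only if there are several deaths before roughly 11 to 18 h, they are unbalanced, and the true effect is well below 44 v 14. In the worst case examined, the current rule moves the chance of a significant benefit by about 10 points, or the false-benefit rate from 0.5% to about 1.4%. With single or balanced deaths the current rule moves that chance by only about 2 to 3 points, and with no deaths nothing changes. The sizes rest on assumed shapes, an assumed 40% shortening and assumed deaths; the direction does not. It is a cheap improvement to the plan, and nothing here suggests that excess deaths on L-citrulline are expected.

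**What to change.** Before unblinding:

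- Make existing rule (2) the primary Wilcoxon scoring: a child who dies before hospital discharge or Day 28 is ranked no better than any survivor.
- State whether a death after discharge but before Day 28 is included; the present wording leaves this open.
- Enter 28 days for these deaths in the Hodges-Lehmann interval.
- Keep observed length and exclusion of deaths as sensitivity analyses.
- In the re-estimation text (SAP 1.4: "Only the re-estimated variance values will be used for the sample re-calculation"; likewise Protocol 7.4), say that the variance is that of observed durations. Otherwise one death could raise the sample size from 92 to about 235-249 per group.

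No further survival analysis is required.

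**Cost.** The primary scoring rule changes in Protocol 7.1.4 and SAP 4.4.1 and 4.8, with one added sentence for the re-estimation. The EU protocol and the external re-estimation document, neither of which was available here, would have to agree. No new data are needed. The endpoint becomes partly a mortality measure, a child weaned early who later dies of another cause also gets the worst rank, and the result is less favourable if early deaths fall mainly on L-citrulline.
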